#### **9.2.3.1.5 Pregnancy and Lactation**

Details of all pregnancies and/or lactation in female subjects and female partners of male subjects will be collected after the start of study treatment and until 6 weeks after the last dose of AMG 420 or in a male subject's female partner through 14 weeks after the last dose of AMG 420.

If a pregnancy is reported, the investigator is to inform Amgen within 24 hours of learning of the pregnancy and/or lactation and is to follow the procedures outlined in [Section 12.5](#). Amgen Global Patient Safety will follow-up with the investigator regarding additional information that may be requested.

Abnormal pregnancy outcomes (eg, spontaneous abortion, fetal death, stillbirth, congenital anomalies, ectopic pregnancy) are considered serious adverse events.

Further details regarding pregnancy and lactation are provided in [Section 12.5](#).

#### **9.2.3.1.6 Safety Monitoring Plan**

Subject safety will be routinely monitored as defined in Amgen's safety surveillance and signal management processes.

#### **9.2.3.2 Vital Signs**

The following measurements must be performed: systolic/diastolic blood pressure, heart rate, respiratory rate, and temperature. Subject must be in a supine position in a rested and calm state for at least 5 minutes before blood pressure assessments are conducted. If the subject is unable to be in the supine position, the subject should be in most recumbent position as possible. The position selected for a subject should be the same that is used throughout the study and documented on the vital sign eCRF. The temperature location selected for a subject should be the same that is used throughout the study and documented on the vital signs eCRF. Record all measurements on the vital signs eCRF.

#### **9.2.3.3 Electrocardiograms (ECGs)**

Subject must be in supine position in a rested and calm state for at least 5 minutes before ECG assessment is conducted. If the subject is unable to be in the supine position, the subject should be in most recumbent position as possible. ECGs should be performed in a standardized method, in triplicate, and run consecutively (ie, approximately 60 seconds apart), prior to blood draws or other invasive procedures. Each ECG must include the following measurements: QRS, QT, QTc, RR, and PR intervals.

- $\geq 3$  baseline ECGs collected  $\geq 30$  minutes apart, with each baseline ECG in triplicate run consecutively (ie, approximately 60 seconds apart) [ie, total  $\geq 9$  ECGs]
- Single ECGs at time points after dosing

The Baseline ECG QTc (defined as the average of the individual baseline ECGs), should not be  $> 470$  msec (applying Fridericia correction). Baseline is defined as predose assessments from cycle 1 day 1. The investigator or designated site physician will review all ECGs. ECGs will be transferred electronically to an ECG central reader for analysis per Amgen instructions. Once signed, the original ECG tracing will be retained with the subject's source documents. At the request of the sponsor, a copy of the original ECG will be made available to Amgen. Standard ECG machines should be used for all study-related ECG requirements.

#### **9.2.3.4 Vital Status**

Vital status must be obtained for all subjects within the limits of local law. This includes subjects who may have discontinued study visits with or without withdrawing consent and should include interrogation of public databases, if necessary. If deceased, the date and reported cause of death should be obtained.

#### **9.2.3.5 Other Safety**

##### **9.2.3.5.1 Pulse Oximetry**

Oxygen saturation will be measured using a standard pulse oximeter. The subject must be in a rested and calm state for at least 5 minutes before pulse oximetry assessments are completed.

##### **9.2.3.5.2 Peripheral Neuropathy**

The peripheral neuropathy assessment should be done at screening and time points specified in the Schedule of Activities ([Section 2.2](#)). All assessments must be reported on the corresponding eCRF page (see [Section 12.16](#)) for peripheral neuropathy assessment tool. Assessments will include historical information on neuropathy symptoms, including relationship to prior anti-MM therapies, severity and duration of symptoms.

#### **9.2.4 Clinical Laboratory Assessments**

Refer to [Section 12.2](#) for the list of clinical laboratory tests to be performed and to the Schedule of Activities ([Section 2.2](#)) for the timing and frequency.

The investigator is responsible for reviewing laboratory test results and recording any clinically relevant changes occurring during the study in the Event eCRF. The investigator must determine whether an abnormal value in an individual study subject represents a clinically significant change from the subject's baseline values. In general, abnormal laboratory findings without clinical significance (based on the investigator's judgment) are not to be recorded as adverse events. However, laboratory value changes that require treatment or adjustment in current therapy are considered adverse events. Where applicable, clinical sequelae (not the laboratory abnormality) are to be recorded as the adverse event.

All protocol-required laboratory assessments, as defined in [Section 12.2](#), must be conducted in accordance with the laboratory manual and the Schedule of Activities ([Section 2.2](#)).

[figure not shown]
#### 9.2.4.1 Pregnancy Testing

[figure not shown]
A highly sensitive (urine or serum) pregnancy test should be completed at screening and within 7 days of initiation of investigational product for females of childbearing potential. In the case of a positive urine result. A serum pregnancy test should be performed for confirmation.

[figure not shown]
Note: Females who have undergone a bilateral tubal ligation/occlusion should have pregnancy testing per protocol requirements. (If a female subject, or the partner of a male subject, becomes pregnant it must be reported on the Pregnancy Notification Worksheet, see [Figure 12-2](#)). Refer to [Section 12.5](#) for contraceptive requirements.

Additional pregnancy testing (serum or urine) during treatment with protocol-required therapies will be performed as indicated in [Section 2.2](#) and at the safety follow-up.

Additional on-treatment pregnancy testing may be performed at the investigator's discretion or as required per local laws and regulations.

**9.2.5 Pharmacokinetic Assessments**

[figure not shown]
All subjects enrolled will have pharmacokinetic samples assessed.

[figure not shown]
[figure not shown]
Whole blood samples of approximately 2 mL will be collected for measurement of serum concentrations of AMG 420 as specified in the Schedule of Activities ([Section 2.2](#)).

Instructions for the collection and handling of biological samples will be provided by the sponsor. The actual date and time (24-hour clock time) of each sample will be recorded.

**9.2.6 Pharmacodynamic Assessments**

Venous blood samples of approximately 20 mL per visit will be collected for measurement of AMG 420 response.

### 9.2.9 Biomarker Development

Biomarkers are objectively measured and evaluated indicators of normal biologic processes, pathogenic processes, or pharmacologic responses to a therapeutic intervention.

In oncology, there is a particular interest in the molecular changes underlying the oncogenic processes that may identify cancer subtypes, stage of disease, assess the amount of tumor growth, or predict disease progression, metastasis, and responses to investigational product(s) or protocol-required therapies.

Amgen may attempt to develop test(s) designed to identify subjects most likely to respond positively or negatively to AMG 420 to investigate and further understand multiple myeloma.

Exploratory assays – [REDACTED]  
[REDACTED]  
[REDACTED]  
[REDACTED]

[REDACTED]  
[REDACTED]

## **10. Statistical Considerations**

### **10.1 Sample Size Determination**

Approximately 20 subjects will be enrolled (approximately 10 treated at the 400 µg/day dose level and approximately 10 treated at the 600 µg/day dose level).

The sample size is based on practical considerations and it is consistent with the number of subjects enrolled in a dose expansion cohort of a conventional, oncology phase 1 study. With 10 subjects treated at a dose level/schedule, there is a 65% to 89% probability of observing an adverse event if the true event rate is 10% to 20%.

### **10.2 Analysis Sets, Subgroups, and Covariates**

#### **10.2.1 Analysis Sets**

The analysis of all endpoints, unless noted otherwise, will be conducted on the Safety Analysis Set defined as all subjects that are enrolled and receive at least 1 dose of AMG 420. An overall assessment of safety with monotherapy treatment will be conducted on the Monotherapy Safety Analysis Set defined as all subjects that are enrolled in the study and receive at least 1 dose of AMG 420. The analysis of DLT will be restricted to DLT-evaluable subjects (see [Section 7.4.1](#)). The analysis of DOR will be restricted to subjects with a partial response or better. DLT evaluation analysis set includes subjects complete the DLT evaluable period or experienced a DLT any time during the DLT evaluable period. The PK Analysis Set will contain all subjects who have received at least 1 dose of the investigational product and have at least 1 PK sample collected. These subjects will be evaluated for PK analysis unless the number of data points required for analysis is not enough, or significant protocol deviations have affected the data, or if key dosing or sampling information is missing.

#### **10.2.2 Covariates**

There are no planned covariates in this study.

#### **10.2.3 Subgroups**

Subgroup analyses will be performed for the primary and secondary efficacy endpoints. The baseline variables for the subgroup analyses may include:

- baseline demographics and characteristics:
  - age (< 65, 65-74, ≥ 75 years)
  - sex (female, male)
  - race (White, Asian, other)
- baseline disease characteristics:

- revised International Staging System (ISS) stage (Stage I, Stages II or III)
- BM percent of plasma cells (< 50%, ≥ 50%)
- 
- extramedullary disease (yes, no). Until safety evaluation is complete for 3 subjects with EM disease, imaging evaluation at screening will be used to document EM disease status as described in [Section 9.2.2.6](#). After DLRT confirms safety in setting of EM disease, EM disease status will utilize investigator assignment.
- number of prior lines of therapy (only 3, > 3)
- prior allogeneic HSCT (yes, no)
- refractory to
  - IMiD (yes, no)
  - PI (yes, no)
  - IMiD + PI (yes, no)
  - daratumumab or other CD 38-targeting antibody (yes, no)

In addition, safety in the subgroup of subjects with EM disease will be reviewed.

Subgroup analysis will not be performed if the sample size within a subgroup is too small. Details will be documented in statistical analysis plan

#### **10.2.4 Handling of Missing and Incomplete Data**

The descriptive statistics will identify the extent of missing data. Missing or incomplete dates that are critical to efficacy and safety analysis, for example, death date and adverse event start dates, will be imputed. Detailed imputation rules will be documented in statistical analysis plan.

#### **10.3 Adaptive Design**

The rules for halting enrollment, or dose de-escalation, are based on an mTPI design. The mTPI was developed by [Ji et al \(2010\)](#). The mTPI models the probability of toxicity for each dose level using a Bayesian model where each dose level has the same prior on the probability of toxicity, a Beta (1,1). When subjects are treated at the current dose level, the posterior probability of toxicity is updated using the observed data from this level. Enrollment recommendations are made based on this posterior probability of toxicity, using three toxicity probability intervals (TPI).

- Under-dosing TPI: DLT rate from 0 to < 20%
- Target TPI: DLT rate from 20% to 33%

- Over-dosing TPI: DLT rate > 33%

For the current dose level and after adjusting for the width of each TPI interval, if the DLT rate is most likely in the under-dosing TPI or most likely in the target TPI then the recommendation is to continue enrollment at the current level. If the DLT rate is most likely in the over-dosing TPI then the recommendation is to halt enrollment.

#### **10.4 Statistical Analyses**

The statistical analysis plan will be developed and finalized before database lock. Below is a summary of the timing and methods for the planned statistical analyses. To preserve study integrity, the final analysis will be conducted and reported following the end of study, as defined in [Section 5.3.1](#).

##### **10.4.1 Planned Analyses**

###### **10.4.1.1 Interim Analysis and Early Stopping Guidelines**

###### **10.4.1.1.1 Interim Analyses**

###### **10.4.1.1.1.1 Safety data will be reviewed by the DLRT on an ongoing basis with the possibility of early termination of enrollment, as described in [Section 5.1](#). Dose Level Review Team**

A DLRT will be responsible for monitoring safety and making recommendations regarding termination of enrollment and dose level/schedule changes.

See [Section 12.3](#) for further details of DLRT responsibilities.

###### **10.4.1.2 Primary Analysis**

The primary analysis will occur when the target enrollment is complete and each subject has had the chance to be treated for at least 6 months.

###### **10.4.1.3 Final Analysis**

A final analysis is planned after all subjects have ended the study.

##### **10.4.2 Methods of Analyses**

###### **10.4.2.1 General Considerations**

Descriptive statistics will be provided for selected demographics, safety, PK, pharmacodynamic and biomarker data by dose, dose schedule, and time as appropriate. Descriptive statistics on continuous data will include means, medians, standard deviations and ranges, while categorical data will be summarized using frequency counts and percentages. Time to event endpoints will be summarized with Kaplan-Meier (KM) proportions at select time points, KM quartiles (when estimable), the number of subjects with events, the number of subjects censored, and censoring

reasons. Duration of follow-up for time to event endpoints will be estimated using the reverse Kaplan Meier method (Schemper and Smith, 1996). Point estimates for efficacy endpoints will be accompanied by 2-sided 95% confidence intervals including KM quartiles (Klein and Moeschberger, 1997), KM proportions (Kalbfleisch and Prentice, 1980), and binomial proportions (Clopper and Pearson, 1934). Graphical summaries of the data may also be presented.

#### 10.4.2.2 Efficacy Analyses

Endpoint	Statistical Analysis Methods
Primary	Not applicable for phase 1b.
Secondary	
Tabular summaries of efficacy endpoints will be reported separately by dose level and part.
 
For subjects included in the Safety Analysis Set, the proportion of subjects with BOR of PR or better per IMWG and MRD negativity at the time of CR will be calculated and tabulated. DOR and time to response analyses will be done for subjects who are in Safety Analysis Set and have a best overall response of PR or better. The percentage of subjects with extended TFI of 4 weeks at approximately 6 months and 4 weeks or 8 weeks at approximately 12 months, out of all treated subjects and out of those who are eligible based on response status (only patients with MRD-negative CR at these landmark times are eligible for the extended TFI calculation). If appropriate, KM proportions at select time points, KM quartiles (when estimable) and KM curves will be provided for DOR, PFS, and OS. Descriptive statistics including median and range will be provided for time to response. Listings will be produced for all subjects indicating the MRD negativity, OS, PFS, time to response, and DOR.

Exploratory	Will be described in the statistical analysis plan finalized before database lock

#### 10.4.2.3 Safety Analyses

##### 10.4.2.3.1 Analyses of Primary Safety Endpoint(s)

Endpoint	Statistical Analysis Methods
Primary	
The primary endpoints are safety endpoints. Unless otherwise specified, statistical analyses on safety endpoints will be done using subjects from the Safety Analysis Set, which includes subjects that are enrolled and received at least 1 dose of AMG 420. Descriptive statistics for safety endpoints will be tabulated overall and by dose level and part.
 
Adverse Events
 
Subject incidence of all treatment-emergent adverse events will be tabulated by system organ class and preferred term. The number and percentage of subjects reporting adverse events will be evaluated overall and by AMG 420 dose level and part will also be tabulated by relationship to AMG 420.
 
Tables of adverse events, fatal adverse events, serious adverse events, adverse events leading to withdrawal from investigational product or other

Endpoint	Statistical Analysis Methods
	
protocol-required therapies, and significant treatment-emergent adverse events will also be provided.
 
Dose Limiting Toxicities
 
The analysis of the probability of DLTs will include data from DLT-evaluable subjects (see Section 7.4.1 for definition of DLT-evaluable). The primary analysis will only include DLTs that occur within the first cycle. If DLTs occur outside the first cycle, a sensitivity analysis will be performed where DLTs occurring outside of the specified time interval are included. The number and percentage of subjects reporting DLTs will be evaluated overall and by AMG 420 dose level and part.
 
Clinical Laboratory Tests
 
Clinical chemistry, hematology, and urinalysis data will be listed and reviewed for each subject. Values outside the normal laboratory reference ranges will be flagged as high or low on the listings. Depending on the size and scope of changes in laboratory data, the analyses of safety laboratory endpoints will include summary statistics over time and/or changes from baseline over time. Maximum shifts in grades of selected safety laboratory values between baseline and the worst on-study value may be tabulated.
 
Vital Signs
 
Vital signs data will be listed and reviewed for each subject. Depending on the size and scope of changes, the analyses of vital signs may include summary statistics over time and/or changes from baseline over time.
 
Electrocardiograms
 
Summaries over time and/or changes from baseline over time will be provided for all ECG parameters. Subjects' maximum change from baseline in QTcF will be categorized and the number and percentage of subjects in each group will be summarized. Subjects' maximum post baseline values will also be categorized and the number and percentage of subjects in each group will be summarized. All on-study ECG data will be listed, and select parameters of interest may be plotted.

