#### **7.4 Dose Modification**

##### **7.4.1 Dose-cohort Study Escalation/De-escalation and Stopping Rules**

The DLT evaluation period (ie, DLT-evaluable period) will be the 4 weeks on AMG 420 treatment within the first treatment cycle, starting on day 1 (start of infusion). The DLT evaluation period may also be extended to assess events starting within the window in case the DLT definition is time dependent.

Treatment in AMG 420 cycle 1 will be considered complete and the subject will be DLT evaluable if the subject has completed the DLT evaluation period or experienced a DLT any time during the DLT evaluation period. A subject will be non-DLT evaluable if he/she drops out before completion of the DLT-evaluable period for reasons other than a

DLT. All available safety data for subjects who are non-DLT-evaluable will still be evaluated and considered in DLRT decisions (see also [Section 10.4.1.1.1.1](#)).

See [Section 5.2.1](#) for description of replacement of subjects.

A DLT will be defined as any of the events described below occurring in a subject during the DLT evaluation period unless clearly attributable to causes other than treatment with AMG 420. The CTCAE version 5.0 (see [Section 12.4](#)) will be used to assess toxicities/adverse events with the exception of CRS and TLS (see [Section 7.4.2.1.2.5](#) and [Section 12.12](#) for grading criteria of CRS and TLS, respectively).

- Death not clearly due to the underlying disease or extraneous causes.

Non-hematologic DLTs:

- Non-hematological adverse event grade 3 or higher, EXCEPT:
  - infection responding to antibiotic/anti-infective treatment within 48 hours
  - grade 3 fatigue or asthenia
  - grade 3 headache resolving to  $\leq$  grade 2 within 72 hours
  - grade 3 insomnia resolving to  $\leq$  grade 2 within 7 days
  - grade 3 fever resolving to  $\leq$  grade 2 within 72 hours
  - grade 3 nausea, vomiting, or diarrhea responding if successfully managed with optimal medical support and resolved within 72 hours
  - laboratory parameters of grade  $\geq$  3, not considered clinically relevant, and improved to grade  $\leq$  2 within 72 hours

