For subjects who die during the study, the death date will be recorded on the end of study CRF in the date subject ended study field. Incomplete death dates where only the day of death date is missing will be imputed using the following rules:

Day 1 of the month will be used if year and month indicate that death happened in different month from last known alive date;

One day after last known alive date will be used if death happened in the same month as last known alive date.

The imputed death date will be used in calculation of duration of response, progression-free survival and overall survival.

Dose-limiting Toxicities (DLTs)

Investigators determine whether a TEAE qualifies as a DLT per the definition described in protocol Section 7.4.1. For an adverse event to qualify as a DLT, the start date must be within 28 days from the date of the first dose of investigational product.

Best Overall Response

Best overall response for a subject is the best observed post baseline disease response per the International Myeloma Working Group Uniform Response Criteria for Multiple Myeloma (IMWG-URC). **The detailed algorithm is provided in [Appendix B](#).**

Overall Response Rate (ORR)

ORR refers to the proportion of subjects with an objective response. Objective response refers to any of the following responses per the International Myeloma Working Group Uniform Response Criteria for Multiple Myeloma (IMWG-URC): (sCR, CR, VGPR or PR) Per IMWG-URC, any response requires 2 consecutive assessments made any time before starting any new therapy. Subjects who do not experience a sCR/CR/VGPR/PR or do not have any follow-up tumor assessments will be regarded as non-responders.

Duration of Response (DOR)

Duration of response (DOR) will be calculated for subjects who achieve a PR or better. For such subjects, the duration of overall response is defined as the time (months) from first documentation of response to disease progression or death due to any cause. Dates of progression and censoring will be determined as described for the analysis of PFS.

DOR (in months) = (Earliest date of disease progression, death, censor - Date of first observation of PR or better before confirmation + 1)/30.4

Subjects who have not ended their response at the time of analysis will have DOR censored on the date of their latest evaluable assessment.

Time to response

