9.6.2 Adverse Events

The Medical Dictionary for Regulatory Activities (MedDRA) version 23.0 or later will be used to code all adverse events to a system organ class and a preferred term. The severity of each adverse event will be graded using CTCAE version 5.0 criteria with exception of CRS which will be graded according to adopted grading system in Lee et al, 2014 and TLS graded according to Cairo-Bishop criteria (refer to protocol Appendix 12). Where appropriate the tables will also be presented by worst grade.

Treatment-emergent adverse events will be summarized based on the number (%) of subjects experiencing events by MedDRA SOC and PT. The denominator for the percentage will be based on the number of subjects in the safety analysis set.

The subject incidence of adverse events will be summarized for

- **TEAE**
 - All treatment-emergent AEs
 - Grade 3 or higher treatment-emergent AEs
 - Treatment-emergent SAEs
 - Treatment-emergent AEs leading to interruption of investigational product
 - Treatment-emergent AEs leading to withdrawal of investigational product
 - Fatal treatment-emergent AEs
- **Treatment-related AEs**
 - All treatment-related AEs
 - Grade 3 or higher treatment-related AEs
 - Treatment-related SAEs
 - Treatment-related AEs leading to interruption of investigational product
 - Treatment-related AEs leading to withdrawal of investigational product
 - Fatal treatment-related AEs

The summaries that are displayed by SOC, PT and grade will be ordered by descending order of incidence of SOC, PT and grade with in each SOC for the total group.

Then summary of TEAEs, summary of TEAEs, TESAEs, Treatment-related TEAEs, and Treatment-related SAEs by SOC, PT and Grade will be generated for extramedullary subjects.

The above adverse event tables will not be created if two or fewer subjects experience the adverse event.

Dose Limiting Toxicities

The analysis of the probability of DLTs will include data from DLT-evaluable subjects (see Protocol Section 7.4.1 for definition of DLT-evaluable). The primary analysis will only include DLTs that occur during the DLT evaluation period. If DLTs occur outside the DLT evaluation period, a sensitivity analysis will be performed where DLTs occurring outside of the specified time interval are included. The number and percentage of subjects reporting DLTs will be evaluated overall and by AMG 420 dose level.

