9.7.5 Analyses of Biomarker Endpoints

The analysis of Biomarker will be described and performed by Clinical Biomarker Group.

10. Changes From Protocol-specified Analyses

There are no changes to the protocol-specified analyses.

11. Literature Citations / References

12. Prioritization of Analyses

No Priority of outputs planned for this study

13. Data Not Covered by This Plan

The analysis of Biomarkers (except MRD) is not covered in this plan.

14. Appendices

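### The sensitivity analysis of dose-limiting toxicities outside the window is essentially empty by definition, and the protocol's first-cycle wording disagrees with its own 4-week period and with the SAP

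*Protocol*

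**What the plan says.** **Definition.** Protocol 7.4.1 says the DLT evaluation period "will be the 4 weeks on AMG 420 treatment within the first treatment cycle", counted from day 1. It then builds that period into the endpoint: "A DLT will be defined as any of the events described below occurring in a subject during the DLT evaluation period". The period "may also be extended to assess events starting within the window in case the DLT definition is time dependent". SAP Section 5 (Definitions, Dose-limiting Toxicities) leaves the classification to investigators under the 7.4.1 criteria and adds that "the start date must be within 28 days from the date of the first dose of investigational product".

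**Analysis.** Protocol 10.4.2.3.1 sets the primary analysis with "The primary analysis will only include DLTs that occur within the first cycle" and continues: "If DLTs occur outside the first cycle, a sensitivity analysis will be performed". SAP 9.6.2 keeps this structure but uses the DLT evaluation period in place of the first cycle for both analyses. For events outside it, "a sensitivity analysis will be performed where DLTs occurring outside of the specified time interval are included".

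**Declared changes.** SAP Section 10 states: "There are no changes to the protocol-specified analyses".

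**The concern.** DLTs are listed first among the primary endpoints, and two things look wrong.

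First, the window differs between sections. A cycle is 4 weeks of infusion plus 2 weeks off, so the first cycle is longer than the DLT evaluation period. The SAP changes the wording without saying so.

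Second, the sensitivity analysis asks for DLTs outside a window when being inside the window is part of the definition of a DLT. If nothing can qualify, the report will contain either no such analysis or a blank one. A reader could take that as evidence that there was no late toxicity of DLT type.

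**Working it through.** No power or precision formula applies here. The check is to compare the windows and then ask which events each analysis can contain.

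**Step 1. Window lengths**

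| Source | Wording, in short | Days |
|---|---|---|
| Protocol 7.4.1 | 4 weeks on treatment in cycle 1 | 4 × 7 = 28 |
| SAP Section 5 | onset within 28 days of first dose | 28 |
| SAP 9.6.2 | DLT evaluation period | 28 |
| Protocol 10.4.2.3.1 | first cycle | (4 + 2) × 7 = 42 |

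The 42 days agree with the footnote to Protocol Table 2-1, where day 43 is day 1 of the next cycle. There are thus two distinct windows, 28 and 42 days. They differ by 42 − 28 = 14 days, a factor of 42/28 = 1.5. The only place that uses 42 days is Protocol 10.4.2.3.1.

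**Step 2. Primary analysis**

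Let t be the onset day, and leave the boundary aside.

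- Protocol: a DLT requires t ≤ 28 (7.4.1), and the analysis keeps t ≤ 42 (10.4.2.3.1). Both hold when t ≤ 28.
- SAP: a DLT requires t ≤ 28 (Section 5), and the analysis keeps t ≤ 28 (9.6.2). Both hold when t ≤ 28.

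The sets are the same. The 42-day limit never binds.

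**Step 3. Sensitivity analysis: events added**

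- Protocol: t ≤ 28 and t > 42. Empty.
- SAP: t ≤ 28 and t > 28. Empty.

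The extension in 7.4.1 does not change this. It covers events that start inside the window and need later observation to be classified, such as grade 4 neutropenia, which must last more than 5 days. Those events belong to the primary analysis.

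**Step 4. Boundary cases**

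Two ambiguities keep the SAP set from being strictly empty.

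- Day 29 is the end of infusion in Table 2-1, and it is unclear whether it falls inside 28 days from first dose.
- The protocol period refers to weeks on treatment, so days during an interruption or after an early stop could be read either way. Protocol 7.4.2.1.2.1 says cycle days keep counting during an interruption.

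**Step 5. How much lies outside the window**

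Protocol 5.3.2 anticipates a median treatment period of about 8 months. At the SAP's 30.4 days per month this is 8 × 30.4 = 243 days. The DLT window covers 28/243 = 11.5% of it, and about 215 days lie outside.

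**Step 6. What one late event would show if it could be counted**

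With about 10 subjects per dose level, one event is 10 percentage points. The exact (Clopper-Pearson) 95% interval is 0 to 30.8% for 0/10 and 0.3% to 44.5% for 1/10. This only illustrates the resolution available; it does not predict an event.

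**The case against.** The strongest reply is that this is a wording slip with little effect. The SAP, which gives the detailed analysis, already uses the 4-week period. The DLT analysis is a count and a percentage without a hypothesis test. Late events remain visible: SAP Section 5 counts adverse events as treatment-emergent up to 33 days after the last dose or end of study, whichever is first. SAP 9.6.2 tabulates them as all, grade 3 or higher, serious, treatment-related, leading to interruption or withdrawal, and fatal. The dose level review team also sees all available safety data. All of this stands, and it limits the consequence. It does not give the sensitivity analysis any content.

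Three stronger readings are tempting, and the documents do not support them.

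- **That the plan has three conflicting windows.** Four weeks and 28 days are the same length, and the SAP rule puts the protocol period into operation.
- **That an event on days 29 to 42 is a DLT under the protocol but not under the SAP.** Protocol 10.4.2.3.1 filters DLTs already defined in 7.4.1, so a day-35 onset qualifies under neither. The wording for events outside the first cycle does suggest that its author thought of a DLT as an event type that can occur at any time. That is a reason to clarify it, but it does not override the explicit definition.
- **That one such event could move a cohort from 3/10 to 4/10 and out of the 20% to 33% target interval.** The interval is not a cut-off for the observed proportion. Protocol 10.3 uses a Beta(1,1) prior and divides each interval's posterior probability by its width (0.20, 0.13, 0.67). For 3/10, Beta(4,8) gives 0.161/0.20 = 0.81, 0.357/0.13 = 2.74 and 0.482/0.67 = 0.72. For 4/10, Beta(5,7) gives 0.050/0.20 = 0.25, 0.230/0.13 = 1.77 and 0.719/0.67 = 1.07. The target interval is the most likely in both, so the recommendation is to continue. Table 5-1 also stops at 8 treated subjects.

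**Conclusion.** The concern holds in a limited form. Protocol 10.4.2.3.1 uses a 42-day window where 7.4.1 and the SAP use 28 days, and the SAP's changed wording is not declared. This does not alter the primary DLT count, apart from day 29 and days off infusion. No enrollment decision is shown to change.

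The substantive defect is the sensitivity analysis. As written it is essentially empty in both documents, although about 215 of some 243 anticipated median treatment days lie outside the window. What is lost is a count of late events of DLT severity, not the late events themselves.

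This conclusion rests on reading the definitions in Protocol 7.4.1 and SAP Section 5 literally. The point about the undeclared change also assumes that the protocol's DLT analysis wording was the same in amendment 4, on which the SAP says it is based. The protocol reviewed here is amendment 5, and its stated rationale does not list Section 10.4.2.3.1.

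**What to change.** 1. In Protocol 10.4.2.3.1, refer to the DLT evaluation period of Section 7.4.1 instead of the first cycle, in both the primary and the sensitivity sentence. If the protocol text stays as it is, record the difference in SAP Section 10.
2. In SAP Section 5, apply the 28-day onset limit to the primary DLT analysis only. State whether day 29 counts, and how days during an interruption or after an early stop are treated.
3. Restate the sensitivity analysis in both documents as treatment-emergent adverse events that meet the existing 7.4.1 event criteria, with onset after the DLT evaluation period and up to the end of the treatment-emergent window (33 days after the last dose or end of study, whichever is first). Report it descriptively by dose level.

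The cost is a few sentences and some clinical review. Grade, dates and attribution are already collected, but several 7.4.1 criteria depend on response or resolution within 48 hours, 72 hours or 5 to 7 days, on clinical relevance, and on cause. Later events therefore need to be assessed against them; a data flag alone is not enough. Follow-up after the window will differ between subjects, so time at risk should be shown beside the counts and the result should not be read as a rate over a common period.
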